8.3 PARTICIPANT DATA COLLECTION

We will collect data using digital questionnaires to record patient-reported outcome measures in addition to physiological strength measure. Data collection forms will be used at baseline (pre-intervention) and at all post-intervention intervals.

8.3.1 Clinical Notes

The assessing surgeon will perform a clinical assessment of the patient as part of the routine standard of care. Patients suffering from localised, ulnar-sided wrist pain often experience tenderness, crepitus and DRUJ instability of the affected wrist (Haugstvedt & Søreide, 2017). A clinical exam is routinely performed to determine the site of TFC tenderness; crepitus noted with rotation or deviation; evidence of DRUJ laxity in pronation or supination; "Lift Off" in pronation or supination; and response to carpal grind tests. Notes from clinical examinations are recorded and stored in the patient's medical chart, whether or not the patient is to be involved in any research trial (Appendix 14.3). If the patient consents to study participation, clinical notes recorded by the surgeon at the time of initial assessment will be collected and deidentified to be used in data analysis, to investigate possible relationships between physiological factors and outcome measures.

8.3.2 Demographic Information

Basic demographic information will be obtained from the participant after consent, but prior to random allocation of an intervention. This will include:

1. Age and gender;
2. Hand dominance;
3. Primary occupation type;
4. Sports or recreational activities;
5. Compensation status/insurance;
6. Medical history including smoking status and concomitant medical conditions;
7. Details of current and previous trauma to the affected wrist;
8. Current pain medications;
9. Surgical history of both wrists;
10. History of any interventions or therapies used by patients in an attempt to treat the affected wrist

8.3.3 Patient-Reported Questionnaires

Participants will complete a digital questionnaire at assessment intervals with the help of a research assistant, to record changes to wrist pain and function (Appendix 14.4). The patient-reported surveys comprise the primary and secondary outcome measures specified in section 7, *Study Outcomes*. These questionnaires will be completed by participants at baseline prior to randomisation and at 6 weeks, 12 weeks, and long-term follow-up intervals.

8.3.4 Range of Motion and Strength

Participants will have their active wrist range of motion recorded by a research assistant at all intervals to record any change to wrist movement throughout the study. A manual goniometer will be used to measure wrist flexion, extension, supination, pronation, radial deviation and ulnar deviation. The research assistant will use hydraulic dynamometers/strength gauge to record the participant's average grip and pinch strength. All measures will also be taken on the contralateral wrist.

8.4 TREATMENT INTERVENTIONS

Following the completion of all research data collection and randomisation allocation at the baseline appointment, the participant will have treatment appointments made with the hand therapist and radiologist if necessary.

8.4.1 Hand Therapy

It was deemed unethical to the investigators to have a control group where participants did not receive any treatment at all, as all participants will be patients referred to the surgeons seeking relief of their symptoms.

For this reason, all participants irrespective of the group they are allocated to, will receive hand therapy. The active control group (Group A) will receive only the hand therapy. Hand therapy with a qualified hand therapist will be provided by Extend Rehabilitation (www.extendrehab.com.au) or EKCO Hand Therapy (www.ekco.com.au) at Brisbane Private Hospital. The baseline treatment appointment and the follow-up sessions for all participants at 2- and 6-weeks post intervention will be provided at a subsidised cost of \$180 for the three sessions. The normal cost for patients outside of the research would be \$360 for these three sessions (Appendix 14.5).

Participants will receive a standardised exercise program and advice on pain management including joint protection and activity modification. This therapy protocol will be reinforced with the provision of a participant exercise booklet, vinyl dumbbells and a compliance log (Appendix

14.6). Therapists will undergo a regular in-service training program to ensure that all participants receive standardised treatment.

Routine follow-up appointments will be provided at 2, 6- and 12-weeks post-intervention. Participants having any concerns or queries between clinical visits will have the contact details for the research institute as first point of contact. The research team will advise their consulting surgeon's practice or treating hand therapist clinic so that appropriate advice can be provided. Any deviation from the prescribed treatment protocol will be recorded at follow up research assessments.

8.4.2 Thermoplastic Wrist Splint

All participants in Group B and Group D will be fitted with a standardised design, thermoplastic, volar wrist splint. This will be custom fitted by a qualified Hand Therapist at Extend Rehabilitation or EKCO Hand Therapy, following the baseline hand therapy session. All hand therapists making splints for study participants will be instructed to follow a standardised design protocol to ensure consistency amongst therapists and practices. The splint will be worn for 6 weeks full time (with the exception of washing and when performing prescribed exercises). After 6 weeks, participants may cease splint wear and use as required for symptomatic relief only.

Minor adjustments may be made to alleviate discomfort caused by the splint. Any deviation from the prescribed orthosis design or non-compliance with orthosis use will be recorded at follow up research assessments.

8.4.3 Corticosteroid Injection

A single dose of ultrasound guided intra-articular corticosteroid injection will be provided by radiologists at Brisbane Private Imaging (Brisbane Private Hospital, Brisbane) at the 6 week interval. The steroid (Celestone Chronodose™) and local anaesthetic (Marcain™) combination to be administered, is the current hydrocortisone & local anaesthetic (HCLA) medication routinely used at Brisbane Private Imaging. A standard procedure will be followed:

1. Participant will be asked to lie in a supine position on the examination table with the affected wrist resting comfortably palm side down on the table or across their abdomen.
2. Antiseptic solution will be applied to the skin.
3. A 25 gauge, 38mm needle will be inserted into the dorsal aspect of the TFCC using ultrasound guidance.
4. A mixture of 1 mL of Celestone Chronodose and 1 mL of 0.5% Marcain will be injected into the TFCC.

The injections will be provided by radiologists at Brisbane Private Imaging, at the Brisbane Private Hospital. The treatment will be bulk billed for the participants (Appendix 14.7)

Celestone Chronodose™ (Merck Sharp & Dohme Pty Ltd, Australia) contains 1ml of betamethasone 5.7mg. It has full TGA approval (Appendix 14.8).

Marcaïn™ (AstraZeneca PTY Ltd, Australia) contains the active ingredient bupivacaine hydrochloride monohydrate. It has full TGA approval (14.9).

8.4.4 Treatment Compliance

A hand therapy compliance log will be provided to all participants to record the frequency of exercises performed over the 12 week treatment period. Participants will be instructed to record on the log each time the set of prescribed exercises are performed. At post-intervention assessment intervals, participants will be asked to answer survey questions about their compliance to the prescribed therapy and splint wear if applicable. Data on participant compliance will be analysed to investigate possible correlation to response to treatment.

8.5 STUDY COMPLETION

Patients outside of research studies are routinely assessed by specialist clinicians at the Upper Limb Clinic at 12 weeks following prescribed conservative management. The assessment intervals for the primary end-point of this study are aligned with the routine clinical follow up schedule for patients having conservative TFCC treatment at this clinic. The secondary end point invites research participants to be reviewed at intervals at 6, 12 and 24 months. These longer-term intervals are often part of routine clinical follow up, dependant on the status of the injury.

8.5.1 Primary End-point

Participants will be assessed by their referring surgeon and have outcomes measured by a research assistant at 12 weeks to assess effectiveness of the randomised conservative treatment for treating the injury. Patients who demonstrate no benefit from conservative management, or an aggravation in symptoms may be considered for further conservative treatment or surgical intervention at the surgeon's discretion. Any further treatment received will result in the conclusion of the participant's ongoing study involvement. Assessments will be made at 2 and 6 weeks to monitor compliance to the treatment allocated, complications/adverse events and an interim assessment of treatment outcomes (6 weeks only).

Data Collection Interval	Range	Review Method
Pre-intervention/baseline	≤ 12 months post initial injury	In person at the clinic Surgeon + Researcher + Hand Therapist
2 weeks Compliance & complications	2 weeks +/- 5 days	In person at the clinic Researcher + Hand Therapist
6 weeks Interim Assessment	6 weeks +/- 10 days	In person at the clinic Researcher + Hand Therapist + Surgeon

12 weeks Primary End-Point	2 – 4 months	In person at the clinic Surgeon + Researcher
-------------------------------	--------------	---

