1 PROJECT SUMMARY

TITLE	Conservative management of triangular fibrocartilage injuries
INVESTIGATORS	
Primary: [name] (Principal Investigator), [name], [name], [name], [name]
 
Associate: [name], [name], [name]

OBJECTIVES	
Primary Objective: To determine the efficacy of splint immobilisation and cortisone injection, used in isolation or combination, for the non-operative management of triangular fibrocartilage complex injury.
 
Secondary Objective: To determine the prevalence and factors associated with TFCC tears not benefitting from a course of conservative treatment.

STUDY DESIGN	Randomised control trial
SITES	Brisbane Private Hospital, Brisbane, Australia
NUMBER OF SUBJECTS	180 participants (45 per treatment group) will be recruited in this study
TARGET POPULATION	Adults presenting with clinical and MRI confirmation of isolated TFCC tear, no greater than 12 months from primary injury.
LENGTH OF CLINICAL INVESTIGATION	
It is anticipated that this study will require 50 months from commencement of recruitment (24-month recruitment period) to final data collection and analysis. Study participants will be assessed at baseline (pre-intervention) and post intervention intervals.
 
The primary end point of the study will be 12 weeks post initiation of conservative treatment to determine treatment effectiveness.
 
The secondary end point of the study will be at 24 months to monitor long term outcomes and ascertain rates of re-injury or recurrence of symptoms.

OUTCOMES	
Primary Outcomes:
 
 ▪ Pain and function using Patient Rated Wrist and Hand Evaluation (PRWHE) 
Secondary Outcomes:
 
 ▪ Improvement in symptoms and function using the global rating of change 15-point scale (GRC) ▪ Disability using the abbreviated version of the Disabilities of the Arm, Shoulder and Hand Score (QuickDASH) ▪ Pain and satisfaction using a visual analogue scale (VAS) ▪ Health-related quality of life using the EQ-5D-5L ▪ Grip strength measured using a hydraulic dynamometer ▪ Complications or adverse events

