7.1 PRIMARY OUTCOME

7.1.1 Patient Rated Wrist and Hand Evaluation (PRWHE)

The Patient Rated Wrist and Hand Evaluation (PRWHE) is a patient-reported questionnaire, comprised of pain and function elements specific to wrist conditions. The 15-item questionnaire consists of two subscales designed to measure wrist pain and difficulty in activities of daily living (ADL), to give an overall score of wrist disability. It is one of the most widely used and validated instruments specific for this population.

Patients are asked to rate their pain on four items from 0 (no pain) to 10 (worst pain) and function on 10 items from 0 (no difficulty) to 10 (unable to do), including four broad ADL questions. Questions are specific to the affected wrist and can be used to calculate a total PRWHE score, in which pain and function are equally weighted. The PRWHE has been used to assess wrist-related pain and disability in various populations and its reliability, validity, and responsiveness have been extensively researched and publicized (MacDermid, Wessel, Humphrey, Ross, & Roth, 2007). A change of 14 points will be considered the minimum change to detect a difference with clinical relevance for the population.

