8.5.2 Secondary End-point

Participants will be invited to be assessed by the referring surgeon and research assistant at 6 months, 12 months and 24-month intervals to determine long-term outcomes and ascertain rates of re-injury. If possible, these assessments will be conducted at the Brisbane Hand & Upper Limb Clinic to allow for completion of patient-reported questionnaires as well as strength measurements to be recorded. If the participant is unable to present in person, they will be invited to complete a partial assessment, comprised of only the patient-reported outcome questionnaires, via completion of the digital survey.

Data Collection Interval	Range	Review Method
6 months	5 – 7 months	In person (Surgeon + Researcher) or digital survey via email
12 months	10 – 14 months	In person (Surgeon + Researcher) or digital survey via email
24 months	22 – 26 months	In person (Surgeon + Researcher) or digital survey via email

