Using historical participant retention at the Brisbane Hand and Upper Limb Clinic as a model, an attrition rate of 25% is anticipated. If 134 is the smallest remaining cohort after attrition (75% retention) required to achieve 80% power, the minimum recruitment sample required would be 179. Due to the balanced study design necessitating even group numbers, the target recruitment sample size is 180 participants, with 45 participants allocated to each group.

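### The 12-week primary end-point has no remote fallback for the PRWHE, although the protocol provides one for the same questionnaire at 6, 12 and 24 months

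*Protocol*

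**What the plan says.** Section 7.1.1 defines the primary outcome: "The Patient Rated Wrist and Hand Evaluation (PRWHE) is a patient-reported questionnaire, comprised of pain and function elements specific to wrist conditions". Section 1 fixes its timing: "The primary end point of the study will be 12 weeks post initiation of conservative treatment to determine treatment effectiveness". Section 8.3.3 describes the format at every assessment: "Participants will complete a digital questionnaire at assessment intervals with the help of a research assistant".

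The two visit tables differ in how these data may be collected.

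- **12 weeks (section 8.5.1).** The text reads "Participants will be assessed by their referring surgeon and have outcomes measured by a research assistant at 12 weeks to assess effectiveness". This sentence does not itself require attendance. The restriction comes from the table below it, whose only review method at 12 weeks is "In person at the clinic Surgeon + Researcher", with a window of 2 to 4 months. The 6-week row is also in person only.
- **6, 12 and 24 months (section 8.5.2).** The table gives "In person (Surgeon + Researcher) or digital survey via email", and the text adds: "If the participant is unable to present in person, they will be invited to complete a partial assessment". That partial assessment consists of the patient-reported questionnaires alone, completed through the digital survey.

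Section 8.1.3.3 provides for up to three contact attempts by phone or email after a missed visit. It does not say that the questionnaire may then be completed remotely. Section 9.1 states that "an attrition rate of 25% is anticipated".

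**The concern.** The visit that decides the trial has a narrower collection route than the visits that do not. By offering the emailed survey later on, the protocol already accepts a remotely completed PRWHE as usable and has the means to collect it. Staff who follow the tables have a stated basis for using that route at 6 months but none at 12 weeks. A participant who is away, unwell or unwilling to travel at 12 weeks could then lack a primary score and still supply a 6-month one.

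Two things are at stake. One is precision. The other is selective missingness: participants know their allocation, because section 8.2 has the envelope contents revealed to them, so attendance could depend on allocation or on how the wrist is doing. The documents give no evidence that it does, but an obtained score removes the question for that participant.

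**Working it through.** **Step 1. Compare the rules.**

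| Item | 12 weeks | 6, 12, 24 months |
|---|---|---|
| Instrument | PRWHE, digital, patient-reported | same |
| Default review | in person | in person |
| If unable to attend | nothing provided | emailed questionnaires |
| Window | 2–4 months | 5–7, 10–14, 22–26 months |

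The instrument does not change between the columns. Only the fallback does.

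**Step 2. Reproduce the plan's sample size (section 9.1).** Inputs: f = 0.29, alpha = 0.05, four groups, numerator df = 3, power 80%. Power comes from the noncentral F distribution with noncentrality lambda = f² x N and denominator df = N − 4.

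- At N = 134: lambda = 0.0841 x 134 = 11.2694, denominator df = 130, critical F = 2.6743, power = 0.8013. This matches the plan.
- Inflation for attrition: 134 / 0.75 = 178.7, so 179, taken up to 180. This also matches.

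**Step 3. Position at the planned attrition.** 180 x 0.75 = 135 evaluable, one more than 134; power is 0.805. The 45 expected losses (180 − 135) are already allowed for.

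**Step 4. What a fallback could add.** The documents do not split the 25% by cause, so the share r of the 45 losses that email would recover is an assumption. Evaluable N = 135 + 45r.

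| r (assumed) | Evaluable N | Power |
|---|---|---|
| 0 | 135 | 0.805 |
| 10% | 140 | 0.821 |
| 25% | 146 | 0.838 |
| 50% | 158 | 0.870 |

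The same assumption can be stated as a share of all participants. If 3% to 10% of the 180 miss the 12-week visit but would answer an email, that is 5.4 to 18 scores. If these lie inside the 45 budgeted losses, evaluable N becomes about 140 to 153 and power 0.821 to 0.857.

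**Step 5. Limits of the figures.** They apply to the ANOVA on which section 9.1 is based, where a participant without a 12-week value contributes nothing. Section 9.3 also names linear mixed effects models. If those use all visits, a participant missing only week 12 still contributes in part, and the gain from recovering the score is smaller than tabulated.

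**The case against.** The strongest defence is that the difference between the visits is reasoned. Section 8.5 says patients at this clinic are routinely seen at 12 weeks even outside research, whereas the longer visits are only often routine and depend on the state of the injury. A fallback is needed most where attendance is optional. The window of about two months leaves room to rebook, and three contact attempts follow a missed visit. All of this stands. It should reduce the number lost, but it does not give a non-attender a route to complete the PRWHE.

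A reader might infer three stronger points that the documents do not support.

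- **That remote completion at 12 weeks is prohibited.** It is not; it is simply not provided for.
- **That the trial will fall below 134 because its margin is one participant.** That margin is what remains after 45 losses have been allowed for. Section 9.1 takes its 25% from past retention at the same clinic, so ordinary non-attendance may well be inside it. No passage supports a further loss on top, and none says whether the 25% refers to 12 weeks or 24 months.
- **That email would recover most of the missing data.** Under sections 8.1.3 and 8.5.1, treatment received beyond the allocated programme ends participation. An emailed survey alone would not recover those losses.

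There is also a real cost. Section 8.3.3 has a research assistant helping with the questionnaire, and emailed completion would lack that help at the primary time point of an open-label trial with a subjective outcome. The protocol already accepts this at later visits, but it is a reason to record the mode.

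**Conclusion.** The point holds as a cheap improvement to the primary data collection. The protocol leaves a non-attender at 12 weeks without a stated way to give a primary score, while providing one for the same questionnaire at every later visit. No contradiction between passages and no shortfall in sample size is shown.

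The size of the loss is unknown. Under the plan's own inputs, and on the assumption that email recovers 10% to 50% of the 45 budgeted losses, power would be about 0.82 to 0.87 in place of 0.805. The benefit against selective missingness cannot be quantified from the documents. It depends on whether those who miss the visit differ from those who attend, and on how many of them would reply.

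**What to change.** In the 12-week row of the section 8.5.1 table, keep in-person review as the default. Add that a participant unable to attend will be sent the patient-reported questionnaires as an emailed digital survey, to be completed within the visit window, following the partial-assessment provision of section 8.5.2. Record for each questionnaire whether it was completed in clinic or remotely. Add a sensitivity analysis by mode, for example repeating the primary comparison without the emailed scores. Grip, pinch and range of motion remain in person.

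If the fallback is also offered at 6 weeks, more than a table edit is needed. Section 8.2 has the second envelope opened at that visit, so the protocol must require the 6-week questionnaire to be completed before the envelope is opened.

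The cost is a protocol wording change and one extra data field, since the emailed survey is already planned. The downside is that some 12-week questionnaires will be completed without a research assistant's help.

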8.5.2 Secondary End-point

Participants will be invited to be assessed by the referring surgeon and research assistant at 6 months, 12 months and 24-month intervals to determine long-term outcomes and ascertain rates of re-injury. If possible, these assessments will be conducted at the Brisbane Hand & Upper Limb Clinic to allow for completion of patient-reported questionnaires as well as strength measurements to be recorded. If the participant is unable to present in person, they will be invited to complete a partial assessment, comprised of only the patient-reported outcome questionnaires, via completion of the digital survey.

Data Collection Interval	Range	Review Method
6 months	5 – 7 months	In person (Surgeon + Researcher) or digital survey via email
12 months	10 – 14 months	In person (Surgeon + Researcher) or digital survey via email
24 months	22 – 26 months	In person (Surgeon + Researcher) or digital survey via email

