5 STUDY DESIGN

This study aims to determine if there are differences in the effectiveness and clinical outcomes of various conservative treatments offered to patients who suffer from triangular fibrocartilage complex (TFCC) tears. A four-arm (Section 2.4) factorial, randomised clinical trial will be implemented.

Participants will be randomly allocated to either an active control group or one of three intervention groups. Participants will be asked to complete an electronic questionnaire consisting of outcome measures designed for conditions specific to the hand and wrist. Outcome measures will be administered at baseline (pre-treatment); 6 and 12 weeks (primary end-point); and at 6, 12 and 24 months from baseline (secondary end-point). Compliance and complications will be recorded at all post-intervention intervals, including two weeks after treatment commencement.

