7 STUDY OUTCOMES

Patient-reported pain and function questionnaires will be administered at baseline, 6 and 12 weeks; and 6, 12 and 24 months post baseline. Compliance and adverse events will be recorded at all post-intervention intervals, including 2 weeks after treatment initiation.

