7.2.6 Adverse Events

Any adverse events occurring during the trial will be closely monitored and followed up until the complete resolution of symptoms. This will include all reactions listed for the cortisone injection and any reactions to the thermoplastic splint. These will be checked at each assessment stage and recorded on the adverse events / complication forms. Adverse events may include:

1. Any adverse reaction from the intra-articular corticosteroid injection, including but not limited to those provided in the product information brochure;
2. Any adverse reaction to use of the thermoplastic wrist splint
3. Wrist instability
4. Reinjury of affected wrist
5. Other (including Chronic Regional Pain Syndrome, or hypersensitivity)

Other changes in symptoms and function noted by participants will be noted at each interval in the event that the change noted progresses to an adverse event or complication.

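### Section 8.5.2 words the remote 6-, 12- and 24-month assessment as questionnaires only, which contradicts the rule that complications, including re-injury, are recorded at every interval

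*Protocol*

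**What the plan says.** **Purpose of the long-term visits.** Section 8.5.2 holds the 6-, 12- and 24-month assessments "to determine long-term outcomes and ascertain rates of re-injury". The project summary (Section 1) describes the 24-month secondary end point in similar terms: to "monitor long term outcomes and ascertain rates of re-injury or recurrence of symptoms".

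**Content of the remote visit.** Section 8.5.2 prefers attendance at the clinic. For those who cannot attend, "they will be invited to complete a partial assessment, comprised of only the patient-reported outcome questionnaires, via completion of the digital survey". Its table allows an emailed survey at all three intervals.

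**Recording of complications.** Section 5: "Compliance and complications will be recorded at all post-intervention intervals, including two weeks after treatment commencement". Section 7: "Compliance and adverse events will be recorded at all post-intervention intervals, including 2 weeks after treatment initiation". Section 7.2.6 says of adverse events: "These will be checked at each assessment stage and recorded on the adverse events / complication forms". Its list of events includes wrist instability and "Reinjury of affected wrist".

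**Use of the data.** Section 9.3 reports complication rates as frequencies and compares them, for example with a Pearson chi-square statistic.

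**The concern.** Site staff cannot follow both instructions for a remote participant. Sections 5, 7 and 7.2.6 call for a complication record at that interval. Section 8.5.2, which is the specific instruction for the remote visit, confines it to the outcome questionnaires. The specific instruction is the one likely to decide what is emailed.

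Re-injury and instability are events. As the protocol describes the scales, PRWHE, QuickDASH, the VAS items, EQ-5D-5L and GRC measure pain, function, satisfaction, quality of life and perceived change. None is described as asking whether the wrist has been injured again. A worse score may reflect a re-injury but does not identify one.

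At stake are one named part of the 24-month end point and the long-term complication frequencies. An event that was never asked about cannot be recovered by any later analysis.

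**Working it through.** No figure stated in the plan bears on this point, so the check is a comparison of sections, followed by an illustration under assumed values.

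**Step 1: the sections side by side**

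| Topic | Sections 5, 7 and 7.2.6 | Section 8.5.2, remote visit |
|---|---|---|
| When complications are recorded | Every post-intervention interval | Not mentioned |
| Instrument | Adverse events / complication forms | Outcome questionnaires only |
| Exception for remote visits | None | None stated, but implied by the word *only* |
| Re-injury | A listed adverse event | Named as a purpose of the visit, with no remote means of recording it |

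Section 8.5.1 differs from Section 8.5.2 in this respect: it names complications explicitly as content of the 2- and 6-week assessments.

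**Step 2: how long the gap could last.** The last assessment that must be in person is at 12 weeks (Section 8.5.1). A participant who is remote at all three later intervals would have no scheduled complication form for about 24 − 3 = 21 months, if Section 8.5.2 is followed literally.

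**Step 3: what can be said about size.** Let *r* be the share of remote responders and *p* the true re-injury risk. The protocol gives neither, and it does not say how a remote responder without a form would be counted. All values below are assumptions.

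- *Counted as event-free, with re-injury unrelated to remote response.* The recorded rate is p(1 − r). With p = 10%: r = 10% gives 0.10 × 0.90 = 9.0%; r = 25% gives 0.10 × 0.75 = 7.5%; r = 50% gives 0.10 × 0.50 = 5.0%.
- *Treated as missing, with re-injury unrelated to remote response.* The rate stays at 10% but rests on fewer people. If 180 × 0.75 = 135 remain after the planned 25% attrition, the same three values of r leave 135 × 0.90 = 121.5, 135 × 0.75 = 101.25 and 135 × 0.50 = 67.5 participants with a form.
- *Treated as missing, with re-injury related to attendance.* Take r = 50%. If in-person risk is 15% and remote risk 5%, the true rate is 0.5 × 15% + 0.5 × 5% = 10% and the recorded rate is 15%. With the two risks exchanged, the true rate is again 10% and the recorded rate is 5%.

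The recorded rate can therefore be too low, correct or too high, depending on facts that the documents do not supply.

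**The case against.** A reader might infer that re-injury and adverse events are simply not collected from remote participants, and that the long-term rates are therefore biased downward. The documents do not support this, for several reasons.

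- **Collection is required elsewhere.** Sections 5, 7 and 7.2.6 ask for it at every interval and exempt nobody. One word in Section 8.5.2 does not clearly override them. This stands, and it is why the finding is a contradiction and not a proven omission.
- **The word *only* may be aimed at strength testing.** The preceding sentence says that clinic attendance allows questionnaires and strength measurements, so the remote visit may be partial merely because strength is dropped. This is plausible. Even so, neither sentence mentions complications, so no remote route is specified on that reading either.
- **The survey may already hold complication items.** Section 8.3.3 says the surveys comprise the Section 7 outcomes, which formally include 7.2.6. Section 8.4.4 shows that survey questions go beyond outcome scales, since compliance is asked there. The questionnaire is Appendix 14.4, whose content is not shown. This cannot be excluded. Section 8.3.3 is weak support, because Section 7 also contains grip strength, which no questionnaire measures. If the items do exist, the wording of Section 8.5.2 still needs correcting.
- **Some re-injuries may surface otherwise.** Under Section 8.1.3.2, a participant who chooses outside treatment is invited to a final assessment and may be contacted six months later. This reaches only re-injuries that lead to further treatment.
- **Downward bias presupposes a counting rule.** The protocol nowhere says that participants without a form count as event-free, and denominators are commonly left to the statistical analysis plan. Nor does it suggest that remote response differs by arm. This stands in full.

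**Conclusion.** The contradiction is real. Section 8.5.2, as worded, conflicts with Sections 5, 7 and 7.2.6 and with its own aim of measuring re-injury. If site staff follow it literally, re-injury and late complications go unrecorded for remote responders, and the long-term re-injury rate and complication frequencies are incomplete.

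The conclusion goes no further than that. Whether data would actually be lost depends on the unseen questionnaire and on site practice. The size and direction of any bias cannot be derived, and the percentages above only illustrate assumptions.

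The reach is limited. The 12-week primary end point and the 2- and 6-week checks are in person. Recurrence of symptoms, the other element named with re-injury in the 24-month end point, can be seen largely through PRWHE, which remote participants do complete. This is a modest point about a secondary end point and long-term safety reporting, worth correcting because it is cheap to correct.

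**What to change.** In Section 8.5.2, redefine the remote assessment as the outcome questionnaires *and* a participant-completed adverse events / complication form within the existing digital survey. The form should ask about new injury to the wrist, instability, reactions, and any treatment received since the last contact. If Appendix 14.4 already holds such items, correcting the sentence and pointing to them is enough.

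State that re-injury and complication rates at each long-term interval will be reported among participants whose form was completed at that interval, with that number shown by arm.

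The cost is one amended sentence, one added sentence and a few survey questions. The visit schedule does not change. The small downside is that remote events are self-reported without examination, so they should be flagged as such in the data and in the tables.
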